9.1 Analysis Sets

- The analysis will include the following datasets:
 - Intent-to-Treat (ITT) set: Including all randomized survivors, regardless of their adherence with the entry criteria. This set will be used for the primary analysis of Quality of Life changes and cancer progression.
 - Per-Protocol (PP) set: Including participants who completed the trial according to the protocol without significant deviations. PP set is a subset of ITT set, excluding survivors with major protocol deviations or those who do not complete the trial. This set will be used to summarize efficacy and support sensitivity analyses.

9.2 Analyses Supporting Primary Objective(s)

The primary analysis will focus on quantifying the impact of **Complement Theory on changes in Quality of Life Score (QoLS), measured by the FACT-G instrument**, over the trial period. Assessments will occur at baseline, 3, 6, 9, 12, and 18 months.

- **Statistical Model, Hypothesis, and Method of Analysis**

- Primary Estimand (Change in QoLS):
 - Null Hypothesis (H0): There is no difference in the mean change in FACT-G QoLS between participants in the Complement Theory program and those in the control group at specified time points.
 - Alternative Hypothesis (H1): Participants in the Complement Theory program demonstrate a statistically significant improvement in QoLS compared to the control group.
- Baseline Data Analysis: Baseline demographics and characteristics will be provided and summarized in both treatment and control groups. Standardized mean differences (SMDs) will be calculated as the measure of distance between groups. SMDs of 0.2 to <0.5, 0.5 to <0.8 and ≥0.8 are considered small, medium, and large, respectively. Frequencies and percentage will be provided for the binary variables as well as the categorical variables (Yes/No); mean (standard deviation) and median (range) will be computed for continuous variables.
- Method of Analysis: Mixed models for repeated measures (MMRM) will be utilized to analyze changes in FACT-G scores over time, accounting for within-subject correlations. This model allows for the inclusion of both fixed effects and random effects to account for individual variability. In addition, covariate-time interaction terms will be included to guarantee the best results. The strength of the effect from each covariate will be evaluated

through the statistical test significance, i.e., P value, at 95% confidence interval.

- **Handling of Intercurrent Events of Primary Estimand(s)**

- For participants who discontinue the intervention or are non-adherent, we will employ a treatment policy strategy. This means all data collected will be analyzed as per the initial treatment assignment, regardless of the discontinuation or level of adherence, preserving the intention-to-treat principle.

- **Handling of Missing Data**

- Given the potential for missing QoLS data due to dropout or non-response, a multiple imputation (MI) approach will be adopted. The imputation model will incorporate variables predictive of missingness and outcomes to generate plausible values for missing data.
- Multivariate imputation by chained equation (MICE) will be used, i.e., filling the missing data multiple times based on the effect from other covariates by constructing a multivariate regression model. MI is superior to single imputation, as it accounts for the uncertainty of missing values in a more robust way. The number of imputations will be 10, i.e., 10 datasets with imputed data will be created. Each imputed dataset gives a point estimate of the regression coefficients as well as its standard deviation, which will be combined across the 10 datasets to obtain the final estimate and their 95% CIs.
- MICE is flexible and can accommodate variables of different types, as well as complexities such as bounded scales or survey skip patterns, making it well-suited for patient-reported outcomes like QoLS.

- **Sensitivity Analysis**

- To complement our intention-to-treat (ITT) analysis, a per-protocol analysis will be performed, including only participants who fully adhered to the intervention, to explore the effect of adherence on QoLS improvement.

- **Supplementary Analysis**

- Efficacy Analysis: survivors in the treatment and control group will be compared for the outcome variables. The comparison will be evaluated based on both SMD and P value. SMD greater than 0.2 will be considered as acceptable differences (section 3.3 indicated the definition of SMD). Descriptive statistics will be compared between treatment groups and control groups, and P values will be calculated using ANOVA tests comparing means of continuous variables, Brown-Mood test to compare the medians, and Chi-Square tests for binary and categorical variables. The differences will be considered as statistically significant within 95% confidence interval, i.e., P value less than 0.05.

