1.2 Trial Schema

1.3 Schedule of Activities

- Step 1: Enrollment and Intervention
 - Screening (including baseline assessment)

- Randomization by recruitment to test or control groups
- Informed Consent
- Access to control and test programs
- Regular Assessments up to 18 months
- Step 2: Data Analysis
 - Interim Data analysis will be 3 months, 6 months, 12 months and 18 months data.
- Step 3: Publication
 - Publication on protocol analysis and outcomes data is expected at 12 months and the end of 18 months

Section 2: INTRODUCTION

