The evaluation of our proposed trial, which integrates live coactive coaching with a software solution for cancer survivors, demonstrates a significant favorable balance between minimal risks and anticipated benefits. The residual risks are minimized through tailored safety measures and are outweighed by the expected benefits of improved physical health, decreased symptom burden, and enhanced quality of life.

Supporting this favorable assessment, a substantial body of research not only confirms the safety of exercise but also endorses the significance of physical activity and lifestyle

changes in cancer management. This evidence base, coupled with medical endorsement of physical activity for enhancing survivor outcomes, bolsters confidence in the trial's approach.

To ensure ongoing safety and integrity, risks and benefits will be continuously assessed, adjusting protocols as necessary to safeguard participant well-being. This trial aligns with best practices in cancer treatment and reflects a commitment to advancing survivor care through evidence-based lifestyle interventions.

Section 3: TRIAL OBJECTIVES, ENDPOINTS AND ESTIMANDS

Trial Objective 1: Impact of Complement Theory's Program on Quality of Life

Clinical Question: How does participation in Complement Theory's program affect Quality of Life Scores (as measured by FACT-G) in cancer survivors compared to those receiving standard care?

- Endpoint(s): Measured through change in FACT-G scores which is designed to assess various dimensions of quality of life including pain levels and sleep quality.
- Estimand(s): The mean difference in change in scores between the intervention and control groups at specified time points during and after the intervention period.

Trial Objective 2: Effect on Employee Absenteeism

Clinical Question: How does participation in the Complement Theory program influence the number of leave days taken by employed cancer survivors due to health issues?

- Endpoint(s): Number of leave days (including sick leave, short-term disability, and long-term disability) taken by participants during the trial period.
- Estimand(s): The difference in the average number of leave days between the intervention and control groups over the trial period.

Trial Objective 3: Impact on Employee Presenteeism

Clinical Question: What is the effect of Complement Theory's program on motivation to work and performance review scores among employed cancer survivors?

- Endpoint(s):

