6.1 Schedule of Events

Schedule of events for test/treatment group:

Intervention or Assessment (Test)	Baseline (Day -30 to -1)	Week	Week	Month 1-6 (Every 30 days)	Month 7-18 (Every 30 days)
		1/3/5/7/9/11/13/15/17/19/21/23/...	2/4/6/8/10/12/14/16/18/20/22/24/...		
Live Coactive Lifestyle Coaching		X	X		

- 3-5 days per week, 45 mins each					
Async access to Lifestyle modification content curated by CT		X	X		
Informed Consent	X				
Eligibility Criteria Assessment	X				
Demographic Details	X				
EHR Access Consent	X				
Claims Data Access	X		X		X
QoLS (FACT-G Form)	X		X		X
Weight	X		X		X
Motivation to work	X	X			X
Employee Performance Review	X	X			X
Absenteeism Questions	X	X			X
Claim data validation with				X	X

survivor						
Cancer Progression Status					X	X

Schedule of events for active comparator (control) group:

Intervention or Assessment (Test)	Baseline (Day -30 to -1)	Week	Week	Month 1-6 (Every 30 days)	Month 7-18 (Every 30 days)
		1/3/5/7/9/11/13/15/17/19/21/23/... /47	2/4/6/8/10/12/14/16/18/20/22/24/... /48		
Async access to publically available lifestyle modification guidance		X	X		
Informed Consent	X				
Eligibility Criteria Assessment	X				
Demographic Details	X				
EHR Access Consent	X		X		X
Claims Data Access	X		X		X
QoLS (FACT-G Form)	X		X		X
Weight	X		X		X
Motivation to work	X	X			X
Employee Performance Review	X	X			X
Absenteeism Questions	X	X			X
Claim data validation with survivor				X	X
Cancer Progression Status				X	X

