8.2 Efficacy Assessments and Procedures

Improvement in Quality of Life (QoLS) as measured by FACT-G questionnaire (Trial Objective 1):

- Endpoint: Change in FACT-G scores measuring quality of life
- Assessment Procedures: Administer the above four questionnaires to assess participants' at baseline and specified time points during and after the intervention period.
- Data Collection: Obtain self-reported scores from participants on Quality of Life.

- Analysis: Calculate the mean difference in change in scores between the intervention and control groups at each time point to evaluate the impact of the intervention.

Reduction in Employee Absenteeism (Trial Objective 2):

- Endpoint: Number of leave days taken by employed cancer survivors due to health issues.
- Assessment Procedures: Track the number of leave days (sick leave, short-term disability, long-term disability) taken by participants in both groups throughout the trial period.
- Data Collection: Obtain leave records from participants' employers or self-reported information from participants.
- Analysis: Compare the average number of leave days between the intervention and control groups to assess the impact of the intervention on reducing absenteeism.

Improvement in Employee Presenteeism (Trial Objective 3):

- Endpoints: Motivation to work (self-reported scales/questionnaires), performance review scores (from employer records or self-reported evaluations).
- Assessment Procedures: Administer self-reported scales/questionnaires to assess participants' motivation to work and obtain performance review scores from employer records or self-reported evaluations.
- Data Collection: Collect self-reported data on motivation to work and obtain performance review scores from participants and their employers.
- Analysis: Compare the mean scores of motivation and performance reviews between the intervention and control groups to evaluate the impact of the intervention on enhancing presenteeism.

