8.4 Adverse Events and Serious Adverse Events

A serious adverse event (SAE) in this trial is defined according to the following severity grades:

- Grade 1: Mild discomfort, not interrupting normal activities
- Grade 2: Moderate discomfort, interrupts normal activities but not incapacitating
- Grade 3: Severe, resulting in disability or necessitating medical consultation (SAE)
- Grade 4: Requires hospitalization (SAE)
- Grade 5: Results in death (SAE)

Only events classified as Grade 3, 4, or 5 are considered SAEs within the context of this trial

- Time Period and Frequency for Collecting SAE Information
 - Time period
 - Start: Apr 15, 2024
 - End: Oct 15, 2025
 - Frequency
 - SAEs will be documented as they are reported by participants.
- Recording of SAEs
 - While prior studies suggest minimal evidence of SAEs resulting from exercise, diet, or meditation in cancer survivors, all SAEs encountered during this trial will be meticulously recorded. Participants can report SAEs directly via the app, or coaches may report on their behalf. Reports should include the severity grade, description of the event, and the participant's perspective on whether the SAE was related to trial interventions.
- Follow up of SAEs

- All participants will continue receiving standard care from their healthcare providers. In the event of an SAE, a dedicated physician will be assigned to assess the situation, provide immediate recommendations, and categorize the cause of the SAE based on discussions with the participant. This classification will also be documented.
- Regulatory Reporting Requirements for SAEs
 - SAEs must be reported to the Institutional Review Board (IRB) within 24 hours of the event's identification. Additionally, the Sponsor will ensure prompt notification of all investigators regarding any SAEs, enabling them to inform participants about potential risks and take any necessary precautions.
- The grading of adverse events is aligned with the Common Toxicity Criteria for Adverse Events (CTCAE) standards, which detail adverse events on a scale from 1 to 5. The complete CTCAE documentation is available on the National Cancer Institute's website: [NCI CTCAE Information](#).

Section 9: STATISTICAL CONSIDERATIONS

The analysis will be conducted on all participant data at the end of 3 months, 6 months, 12 months and 18 months (ie. end of the trial).

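### Protocol: the primary FACT-G hypothesis spans several visits, but the plan does not say which MMRM contrast is confirmatory

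*Protocol*

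**What the plan says.** This point concerns the Protocol. In the Combined protocol and SAP, healthcare expenditure is primary and FACT-G is secondary.

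- **Section 3, Trial Objective 1 (estimand):** "The mean difference in change in scores between the intervention and control groups at specified time points during and after the intervention period".
- **Section 8.2 (analysis):** "Calculate the mean difference in change in scores between the intervention and control groups at each time point".
- **Section 9.2 (null hypothesis):** mean FACT-G change does not differ between programme participants and "those in the control group at specified time points". The alternative names no visit. The method is an MMRM of change over time.
- **Section 9.2 (visits):** "Assessments will occur at baseline, 3, 6, 9, 12, and 18 months".
- **Opening of Section 9 (analysis times):** "The analysis will be conducted on all participant data at the end of 3 months, 6 months, 12 months and 18 months". Month 9 is absent.
- **Section 9.6:** an O'Brien-Fleming spending function applies across looks at 3, 6 and 12 months, counted from the start of the trial. The efficacy criterion is a significant quality-of-life gain or, alternatively, better health outcomes, which are not defined.
- **Section 9.7:** FACT-G is sized as a single comparison, one-sided alpha 0.05, 80% power.
- **Section 1.3:** "Publication on protocol analysis and outcomes data is expected at 12 months and the end of 18 months".

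No section names a primary visit, an averaged contrast, a joint test, a testing order or an adjustment across visits. The threshold sentence in 9.2, "The differences will be considered as statistically significant within 95% confidence interval, i.e., P value less than 0.05", belongs to the supplementary comparisons (ANOVA, Brown-Mood, chi-square) and does not select an MMRM contrast.

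**The concern.** An MMRM fitted to five post-baseline visits gives five visit-specific treatment differences and any number of combinations of them. The plan commits to none, so the quantity that decides the primary claim can still be chosen after data are seen.

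The candidates also answer different clinical questions. Month 3 is early in coaching, Month 12 is the end of the intervention and Month 18 is six months after it. A report of a positive primary result could mean any of these. If the favourable visit were picked afterwards, the false-positive rate would exceed the stated 5%.

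The interim rule does not close the gap. A spending function protects one test statistic examined repeatedly, and 9.6 does not say what that statistic is. Its second efficacy trigger, undefined health outcomes, widens the choice further.

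**Working it through.** **The plan's own figure.** Inputs from 9.7: means 70 and 85 (difference 15), one-sided alpha 0.05, power 80%, 1:1 allocation, spread given as a variance of 20.

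n per arm = 2(z₀.₉₅ + z₀.₈₀)²(σ/δ)² = 2(1.645 + 0.842)²(20/15)² = 21.98, so 22 per arm, against 21 stated. This works only if 20 is read as a standard deviation; a literal variance of 20 gives 2 per arm. The stated figure is therefore for one comparison.

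**Inputs for the error across visits.** There are five visits (9.2), four analysis times (opening of Section 9) or two publication points (1.3). The critical value is z = 1.645 (9.7). The documents give no between-visit correlation r of the test statistics, so an exchangeable r from 0.95 to 0.4 is assumed. The value 0.5 has a rationale: if all assessments are equally correlated at ρ, unadjusted changes from a shared baseline have covariance σ²(1 − ρ) and variance 2σ²(1 − ρ), a ratio of 0.5.

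**Reading A: any of k visits could carry the claim, unadjusted.** The false-positive chance is 1 − ∫ φ(u) [Φ((z − √r·u)/√(1 − r))]ᵏ du.

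| Visits | r = 0.95 | 0.8 | 0.5 | 0.4 |
|---|---|---|---|---|
| Five | 8.0% | 11.7% | 16.6% | 18.0% |
| Four (3, 6, 12, 18) | 7.6% | 10.6% | 14.4% | 15.4% |
| Two (12, 18) | 6.3% | 7.5% | 8.8% | 9.1% |

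**Reading B: each analysis time tests only its own visit at the O'Brien-Fleming bound.** Information fractions t = 1/6, 1/3, 2/3, 1 are illustrative, because the documents give no accrual figures. Cumulative spending 2[1 − Φ(1.96/√t)] is 0.0000016, 0.00069, 0.0164 and 0.05, which gives bounds z = 4.66, 3.20, 2.14 and 1.70. Replacing the k equal terms in the formula above by Φ((b_j − √r·u)/√(1 − r)) for the four bounds gives 4.5% (r = 0.95), 5.0% (0.8), 5.6% (0.5) and about 5.7% (0.4). The ceiling at any correlation is the sum of the four tail areas: 0.0000016 + 0.0007 + 0.0162 + 0.0446 = 6.1%.

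**Reading C: one pre-specified contrast, tested at every look under the same spending.** This holds 5% by construction.

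**Does the spending function alone help?** If all five visits are tested at every look with the same bounds, simulation gives 9.5% (r = 0.9), 13.6% (0.7) and 16.8% (0.5), essentially as in Reading A. This simplification ignores that later visits are not yet available at early looks. Under spending, the error therefore depends on whether each look is confined to one contrast.

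**The case against.** Nothing in the Protocol says that one significant visit counts as success. Section 9.2 describes change over the whole trial period with a single alternative hypothesis, which could be read as one overall contrast. The four analysis times in Section 9 nearly coincide with the looks in 9.6. If each look tests its own visit, the existing rule already removes almost all of the inflation (Reading B). The list of visits stands just above the null hypothesis and is its natural referent. A publication timetable is not a success rule.

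Most of this stands, and it rules out stronger conclusions that a reader might draw:

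- **That the plan inflates the error to 8-18%.** This presumes an any-visit rule that the plan does not state.
- **That the plan has no type I error control.** Section 9.6 does provide it across looks.
- **That the time points cannot be identified.** The 9.2 list supplies them. Only Month 9 is in doubt, since it is assessed but is not an analysis time. More frequent FACT-G collection in the 6.1 schedule is not in itself a conflict.
- **That publishing at 12 and 18 months creates two primary claims.** Section 1.3 does not say so.

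The objection does not supply the missing choice. Reading an overall contrast into the MMRM sits badly with Section 8.2, which asks for a difference at each visit. Reading B is hard to square with 9.6, which counts looks from the start of the trial. Section 4.4 defines that start as the first participant's enrolment, so at 3 months only someone enrolled at the very beginning could have a Month 3 visit.

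**Conclusion.** The concern holds as a gap in specification. The Protocol does not say which MMRM treatment contrast is confirmatory for FACT-G and gives no hierarchy or adjustment across visits. The 9.6 boundary is not tied to any contrast and admits a second, undefined trigger.

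At one-sided 0.05 the consequence runs from almost none (about 4.5-5.7% if each analysis time tests its own visit at the bounds) to substantial (6-9% for Months 12 and 18 alone, 8-15% for four visits, 8-18% for five, if any visit could carry the claim unadjusted). These ranges rest on the assumed correlations and, for the bounds, on illustrative information fractions. The text permits readings at both ends, so the actual error rate cannot be stated. The choice cannot be made credibly once unblinded data have been analysed.

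**What to change.** Before unblinded data are analysed:

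1. In Sections 3, 8.2 and 9.2, name one confirmatory MMRM treatment contrast, for example the Month 12 difference in FACT-G change from baseline. Month 18, a visit-averaged contrast, a joint test or a fixed hierarchy would also control the error. Report the other visits as supportive.
2. In 9.6, tie the efficacy boundary to that contrast alone and remove the alternative trigger of better health outcomes. Base information fractions on participants with data for that contrast, not on months since the trial began.
3. State whether Month 9 is an analysis visit, so that 9.2 and the opening of Section 9 agree.

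These are text changes, with no added patients or visits. Power is not a constraint on the plan's own figures: with 51 per arm, a difference of 15 and 20 read as the SD, a t test of one contrast at one-sided 0.05 has about 98% power.

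There are two costs. Significance at another visit can no longer be claimed as primary success. Looks at 3 and 6 months after trial start cannot test a Month 12 or Month 18 contrast for efficacy, because no participant will have reached those visits.

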7.1 Discontinuation of Trial Intervention

Criteria for Permanent Discontinuation of Trial Intervention

- Participant Withdrawal: Participants may voluntarily withdraw from the trial intervention at any time for any reason. This may include personal preferences, intolerable side effects, or changes in health status that make continued participation undesirable.
- Adverse Events: Participants experiencing serious or intolerable adverse events related to the trial intervention may be discontinued from further participation in the intervention. Adverse events will be carefully monitored and managed.
- Disease Progression: If a participant experiences disease progression or other significant changes in health status that render the trial intervention ineffective or inappropriate, discontinuation from the intervention may be warranted. This may include worsening of cancer symptoms, disease recurrence, or development of new medical conditions impacting intervention efficacy.

- Non-Adherence: Participants who fail to adhere to the trial intervention protocol, including non-compliance with usage instructions for the Live coaching and software, will be discontinued from further participation in the intervention.
- Ineligibility: If a participant is found to be ineligible for continued participation in the trial intervention due to newly discovered medical conditions or other factors, discontinuation from the intervention may be necessary.

Participants who discontinue trial intervention may or may not be allowed to continue the trial, depending on the specific circumstances. In some cases, participants may continue to undergo follow-up assessments and data collection even if they discontinue the intervention. This allows for the evaluation of secondary outcomes, long-term effects, and safety monitoring following discontinuation of the intervention.

Temporary Discontinuation or Interruption of Trial Intervention

- Acute Medical Events: Temporary discontinuation may be warranted in the event of acute medical events such as hospitalization, surgery, or serious adverse reactions requiring immediate medical attention.
- Non-Urgent Medical Procedures: Temporary interruption may be necessary for non-urgent medical procedures that temporarily interfere with the participant's ability to engage with the trial intervention, such as elective surgery or diagnostic procedures.

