- Serious Adverse Events: Temporary discontinuation may be indicated in the presence of serious adverse events related to the trial intervention, pending further evaluation and resolution of symptoms.
- Participant Preference: Temporary discontinuation may occur at the participant's request due to personal reasons, travel, or other temporary circumstances that interfere with intervention adherence.

During the period of temporary discontinuation or interruption of trial intervention, the following steps will be taken:

- Documentation: The reason for temporary discontinuation or interruption will be documented in the participant's trial documentation, including the date and duration of interruption.
- Participant Education: Participants will be informed of the temporary discontinuation or interruption and provided with guidance on when and how to resume the intervention, as well as any necessary precautions or restrictions.
- Continued Trial Participation: Participants may continue in the trial during the period of temporary discontinuation or interruption, depending on the nature of the event.
- Assessments: Depending on the nature and duration of the temporary discontinuation, certain trial assessments may continue as scheduled, while others may be temporarily suspended or deferred. Assessments relevant to safety monitoring or primary endpoints will be prioritized, while non-essential assessments may be postponed until the participant resumes the intervention.

Rechallenge

- Participants will be allowed to rejoin the trial if medically permitted.

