7.2 Participant Withdrawal from the Trial

1. Voluntary Withdrawal: Participants have the right to withdraw from the trial at any time for any reason without facing any consequences.
2. Inability to Continue: Participants may withdraw if they become unable to continue participating in the trial due to medical reasons, such as worsening health status, or other personal circumstances.
3. Non-compliance: Participants may be withdrawn from the trial if they fail to adhere to the study protocol or follow the instructions provided by the research team.
4. Safety Concerns: Participants may be withdrawn from the trial if there are safety concerns identified during the course of the study, such as the development of

serious adverse events or medical conditions that may compromise their well-being.

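### The primary estimand uses treatment policy, but the protocol does not require FACT-G after permanent discontinuation and allows removal from the trial for non-compliance

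*Protocol*

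**What the plan says.** Section 9.2 of the Protocol sets the intercurrent-event strategy for the primary FACT-G estimand: "For participants who discontinue the intervention or are non-adherent, we will employ a treatment policy strategy". It explains this as analysing whatever data were collected according to initial assignment. On timing it says "Assessments will occur at baseline, 3, 6, 9, 12, and 18 months".

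Section 7.1 governs what happens after permanent discontinuation of the intervention: "Participants who discontinue trial intervention may or may not be allowed to continue the trial, depending on the specific circumstances". It goes on: "In some cases, participants may continue to undergo follow-up assessments and data collection even if they discontinue the intervention". The reason given is "This allows for the evaluation of secondary outcomes, long-term effects, and safety monitoring following discontinuation of the intervention". Under temporary interruption, a separate part of 7.1, the rule is firmer: "Assessments relevant to safety monitoring or primary endpoints will be prioritized".

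Section 7.2 item 3 concerns leaving the trial altogether: "Participants may be withdrawn from the trial if they fail to adhere to the study protocol".

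For missing scores, 9.2 plans multiple imputation by chained equations with 10 imputations: "The imputation model will incorporate variables predictive of missingness and outcomes to generate plausible values for missing data". The only sensitivity analysis named for the primary outcome is a per-protocol analysis restricted to full adherers.

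**The concern.** A treatment policy estimand counts the outcome after the intercurrent event as it actually occurs. It can be estimated from observed data only if outcomes are still collected after participants stop or cease to adhere. Sections 7.1 and 7.2 let trial staff decide, case by case, whether that happens for exactly the two events that 9.2 names.

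The route is short. Section 7.1 says non-adherent participants will be taken off the intervention, after which follow-up is discretionary; 7.2 then permits removal from the trial. The grounds for discontinuation in 7.1 include adverse events and disease progression, so the decision not to follow someone may be related to their quality of life.

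The loss may also differ by arm. The 7.1 non-adherence rule refers to use of the live coaching and software, while section 6.3 leaves control participants free to use the app as they like. Greater loss in the coaching arm is therefore a risk, though the documents do not state it as a fact.

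At stake is whether the result reported as treatment policy is one. If the missing off-programme scores are filled with values typical of people still being coached, the analysis moves towards the effect in those who stay on.

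**Working it through.** **1. Passages side by side**

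| Situation | Collection rule | Source | Meets the needs of 9.2? |
|---|---|---|---|
| Temporary interruption | Primary-endpoint assessments given priority | 7.1 | Largely |
| Stop and resume at will | Participant may resume | 6.3 | Less affected |
| Permanent discontinuation | Follow-up discretionary, in some cases only | 7.1 | No |
| Non-compliance | Removal from the trial permitted | 7.2 item 3 | No |

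The gap is confined to the last two rows. The Combined protocol and SAP, whose primary outcome is healthcare expenditure, has the same pairing in its sections 7.1, 7.2 and 9.2.

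**2. Whether other parts of the plan close the gap**

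- The ITT set (9.1) keeps every randomised participant in the analysis, but it does not create scores that were never collected.
- Multiple imputation models the missing values. Attendance logs exist (6.7) and could be used, but 9.2 does not say that discontinuation status enters the model. If few discontinuers are followed, there is little data from which to learn their course.
- The per-protocol analysis excludes the people in question, so it cannot reveal the bias.
- The quality limits in 11.1 trigger review and do not require follow-up. With N = 146:
  - Premature discontinuation, 5%: 0.05 × 146 = 7.3. Seven does not cross the limit (7/146 = 4.8%); eight does (8/146 = 5.5%).
  - Endpoint data not collected, 15%: 0.15 × 146 = 21.9, crossed at 22 (22/146 = 15.1%).

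**3. The plan's own figures**

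Section 9.7 needs 102 evaluable and allows 30% drop-off: 102/0.70 = 145.7, so 146, or 73 per arm. This reproduces. The FACT-G row assumes 70 versus 85, a difference of 15. Its stated 42 in total is approximately reproduced only if the spread of 20 is read as a standard deviation: the one-sided normal formula at alpha 0.05 and 80% power gives 22 per arm, or 44.

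**4. Illustrative size of the bias**

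Let p be the fraction of the coaching arm that stops and is not followed, and k the share of the 15-point effect those people keep. Assume they are imputed like the people retained, and that loss in the control arm introduces no bias.

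- True treatment policy difference: 15 × [(1 − p) + p × k]
- Difference after imputation: 15
- Overstatement: 15 × p × (1 − k)

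| p | k = 1 | k = 0.5 | k = 0 |
|---|---|---|---|
| 0.05 | 0 | 0.375 | 0.75 |
| 0.10 | 0 | 0.75 | 1.5 |
| 8/73 = 0.110 | 0 | 0.82 | 1.64 |
| 0.20 | 0 | 1.5 | 3.0 |
| 0.30 | 0 | 2.25 | 4.5 |

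The 8/73 row takes the first count that crosses the 5% limit and places all eight in the coaching arm, unfollowed. The 0.30 row borrows the overall drop-off allowance from 9.7 as an outer bound; it does not predict how many discontinuers would go unfollowed.

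**5. Power**

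Power is not the issue. With 73 per arm, SD 20 and one-sided 0.05, power is 99.6% for a true difference of 14.25 (p = 0.05, k = 0) and 93.7% for 10.5 (p = 0.30, k = 0).

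**6. A secondary point in 9.9**

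One row of the deviation table codes as Major the case of a participant who has met the criteria for stopping study treatment but is kept in the study. Read literally, this makes the follow-up permitted by 7.1 a major deviation. It may instead mean continuing the intervention. It affects the per-protocol set and the 10% quality review, and leaves the ITT analysis unchanged. Missed sessions and late make-up sessions are coded only as Minor.

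**The case against.** The strongest case on the other side is that this is an incomplete specification and not a contradiction. Sections 7.1 and 7.2 permit loss but do not order it. Section 6.7 lists patient-reported outcomes, including the primary metric, among the mandatory documents. Section 8.2 has FACT-G collected during and after the intervention period with no exemption for people who stop. Section 7.1 lets participants rejoin if medically permitted. The sentence giving secondary outcomes and safety as the purpose of follow-up appears unchanged in the Combined protocol and SAP, where FACT-G is secondary, so it may simply be carried-over text. Discontinuation status is an obvious candidate for the imputation model, and nothing excludes it.

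Part of this stands. The failure to name the primary outcome is weak evidence by itself, and FACT-G is covered by the 7.1 rule only through its general wording. The size of the bias rests on assumptions throughout: 0.82 to 1.64 points is about 5% to 11% of 15, it would shrink once scores from before discontinuation and attendance enter the imputation model, and its direction depends on unfollowed participants doing worse. The 9.9 row has a harmless reading.

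The main point is unaffected. General scheduling and record-keeping text does not override a specific rule on what happens after permanent discontinuation. Analysing all collected data says how scores are used and leaves open whether they are sought. A good imputation model still needs some observed off-programme scores to learn from.

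**Conclusion.** The concern holds and should be fixed. Following 7.1 and 7.2 as written can leave the primary estimand without the scores on which it is defined, and no other provision requires those scores to be collected. Confidence is high on the conflict in the text.

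The overstatement is an illustration only: 0.75 to 1.5 points on a planned 15 if 10% of the coaching arm is unfollowed and keeps half to none of the effect, and zero if they keep all of it. It rests on assumed p and k, on imputation that treats these people like those retained, and on no bias from control-arm loss. The plan specifies none of these. The 9.9 row is a secondary ambiguity and does not bear on the ITT result.

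**What to change.** - **7.1:** Separate stopping the intervention from ending outcome collection. State that participants who stop or are non-adherent are still asked for FACT-G at months 3, 6, 9, 12 and 18 (the 9.2 time points), unless they withdraw consent or leave the trial under 7.2 items 2 or 4. Name the primary outcome as a purpose of that follow-up.
- **7.2 item 3:** Remove non-compliance as a ground for ending outcome collection.
- **9.9:** Reword the discontinuation row so that outcome follow-up after stopping the intervention is not a deviation.
- **Reporting:** Show by arm how many stopped and how many of those gave FACT-G afterwards.

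When the intervention itself should stop is for the sponsor to decide; sections 6.3, 7.1, 7.2, 9.2 and 9.9 must be reconciled with one another.

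The cost is wording in three places, one table, and at most five FACT-G requests per person who stops. The full section 6.1 schedule would be far heavier: 24 even-week entries to week 48 plus 12 monthly entries in months 7 to 18. The downside is that people who have stopped still receive questionnaires, and some may no longer use the app. Those requests would need email or phone, which 7.3 already provides for. The fix is partial, because people leaving for health or safety reasons under items 2 and 4 may still be lost. The by-arm table should therefore count them as well.
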